4.4.2 Secondary Immunology Endpoints

4.4.2.1 Tetanus Toxoid Adsorbed Vaccine Response Measured 4 weeks after Vaccine Administration

The proportion of patients in Groups A and B with a positive response (IgG) to TT vaccine measured 4 weeks after TT vaccine administration will be compared. Positive response is defined as follows (this differs from the definition of response used for the 8-week assessment above):

- For patients with pre-immunization tetanus antibody titers <0.1 IU/mL, a positive response to the booster TT immunization is defined as an antibody titer ≥ 0.2 IU/mL measured 4 weeks after immunization.
- For patients with pre-immunization tetanus antibody titers ≥ 0.1 IU/mL, a positive response to the booster TT immunization is defined as a 2-fold increase in antibody titers measured 4 weeks after immunization compared with pre-immunization levels.

The number and proportion of patients with a positive response to TT adsorbed vaccine will be presented by treatment group. The difference between treatment groups A and B in positive response rates and the associated 95% CI will also be presented using a normal approximation method.

Levels of anti-tetanus antibody in patients in Groups A and B measured 4 weeks after a booster vaccine will be summarized descriptively by treatment group using the same summary statistics as presented above for the primary immunology endpoint at 8 weeks after vaccine administration.

4.4.2.2 23-Valent Pneumococcal Polysaccharide Vaccine and Pneumococcal Conjugate Booster

The 23-PPV vaccine is assessed by measurement of 23 anti-pneumococcal antibody serotypes (1, 2, 3, 4, 5, 6B, 7F, 8, 9N, 9V, 10A, 11A, 12F, 14, 15B, 17F, 18C, 19A, 19F, 20, 22F, 23F, and 33F). The 13-PCV vaccine acts as a booster to the 23-PPV vaccine, and the 13-PCV vaccine is assessed by measurement of 13 anti-pneumococcal antibody serotypes (1, 3, 4, 5, 6A, 6B, 7F, 9V, 14, 18C, 19A, 19F, and 23F). At the time this SAP was prepared, it is known that no data can be reported for Serotype 6A. Therefore only 12 of the planned 13 serotypes can be analysed for the 13-PCV booster, and all of these 12 serotypes are included in the 23 serotypes which make up the 23-PPV assessments.

Group A1: Patients in Group A1 receive the 23-PPV vaccine at Week 16 and also the 13-PCV booster vaccination 4 weeks later at Week 20. All 23 serotypes are assessed immediately prior to 23-PPV vaccination at Week 16, again prior to the 13-PCV “booster” 4 weeks later at Week 20, and then again 4 weeks after that at Week 24.

Group A2: Patients in Group A2 receive the 23-PPV vaccine at Week 16, but do not receive the 13-PCV “booster”. All 23 serotypes are assessed immediately prior to 23-PPV vaccination at Week 16, again 4 weeks later at Week 20 and again 4 weeks after that at Week 24.

Group B: Patients in Group B follow a similar schedule to Group A2, but earlier in the study. They receive the 23-PPV vaccine at Week 4, and do not receive the 13-PCV “booster”. All 23 serotypes are assessed immediately prior to 23-PPV vaccination at Week 4, again 4 weeks later at Week 8 and again 4 weeks after that at Week 12.

Summaries will show the following groups separately: Group A1, Group A2, Group A (Groups A1 and A2 combined), and Group B. Pairwise between-group comparisons will show:

- Group A1 versus Group A2
- Group A1 versus Group B
- Group A2 versus Group B
- Group A (A1 and A2 combined) versus Group B

Note that the first 3 of the 4 comparisons above, which involve treatment groups A1 and A2 separately, should be interpreted with some caution, since patients were not assigned to these 2 treatment groups randomly (patients were randomized to Group A or

Group B, and within Group A were non-randomly assigned to Group A1 or A2, based on seasonality considerations).

A positive response against a serotype is defined as developing either a 2-fold increase in level or a > 1 $\mu\text{g/mL}$ rise in level, compared with pre-immunization levels.

At 4 weeks after the 23-PPV vaccine, the number and proportion of patients in Groups A1, A2, A (A1 and A2 combined), and B with a positive response (as defined above) against each of the 23 serotypes will be presented. For the same 4 pairwise between-group comparisons described earlier in this section, pairwise between-group differences in positive response rates and the associated 95% CI will also be presented for each serotype, using a normal approximation method.

At 4 weeks after the 23-PPV vaccine, the number and proportion of patients in Groups A1, A2, A (A1 and A2 combined), and B with positive responses (as defined above) against at least 2 of the 23 serotypes will also be presented. For the same 4 pairwise between-group comparisons described earlier in this section, pairwise between-group differences in response rates and the associated 95% CI will also be presented, using a normal approximation method.

At 4 weeks after the 23-PPV vaccine, the number and proportion of patients in Groups A1, A2, A (A1 and A2 combined), and B with positive responses (as defined above) against at least 50% of the serotypes (≥ 12 of 23) will also be presented. For the same 4 pairwise between-group comparisons described earlier in this section, pairwise between-group differences in response rates and the associated 95% CI will also be presented, using a normal approximation method.

At 8 weeks after the 23-PPV vaccine (which is 4 weeks after Group A1 patients received the 13-PCV booster), the number and proportion of patients in Groups A1, A2, A (A1 and A2 combined), and B with a positive response (as defined above) against each of the 23 serotypes will be presented. For the same 4 pairwise between-group comparisons described earlier in this section, pairwise between-group differences in positive response rates and the associated 95% CI will also be presented for each serotype, using a normal approximation method.

Levels of anti-pneumococcal antibodies ($\mu\text{g/mL}$) against each of the 23 different serotypes in patients in Groups A1, A2, A (A1 and A2 combined), and B measured 4 weeks and 8 weeks after administration of 23-PPV (which is 4 weeks after Group A1 patients received the 13-PCV booster) will be summarized descriptively by group using the same summary statistics as presented in Section 4.4.1 for the primary immunology endpoint.

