3.4 OUTCOME MEASURES

3.4.1 Primary Immunization Outcome Measure

The primary outcome measure is the proportion of patients in Groups A (i.e., combined Groups A1 and A2) and B with a positive response (IgG) to TT vaccine measured 8 weeks after TT vaccine administration.

For patients with pre-immunization tetanus antibody titers <0.1 IU/mL, a positive response to the booster immunization is defined as an antibody titer ≥0.2 IU/mL measured 8 weeks after immunization. For patients with pre-immunization tetanus antibody titers ≥0.1 IU/mL, positive response to the booster immunization is defined as a 4-fold increase in antibody titers compared with pre-vaccination levels measured 8 weeks after immunization. Pre-immunization levels are those obtained immediately prior to administration of a vaccine.

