3.4.2 Secondary Outcome Measures

The secondary outcome measures are as follows:

- TT response:
 - The proportion of patients in Groups A (A1 and A2) and B with a positive response (IgG) to TT vaccine measured 4 weeks after TT vaccine administration.
 - The proportion of patients in Groups A (A1 and A2) and B with a 2-fold increase in tetanus antibody titers, or with tetanus antibody titers ≥ 0.2 IU/mL, measured 4 weeks after the immunization of patients with pre-immunization tetanus antibody titers ≥ 0.1 IU/mL or with pre-immunization tetanus antibody titers < 0.1 IU/mL, respectively.
 - Mean levels of anti-tetanus antibody in patients in Groups A (A1 and A2) and B measured immediately prior to and 4 weeks after a booster TT vaccine.
- Pneumococcal vaccine response:
 - The proportion of patients in Groups A (A1 and A2) and B with positive antibody responses against an individual pneumococcal serotype measured 4 weeks after the 23-PPV (23 serotypes). (A positive response against a serotype is defined as developing a 2-fold increase in antibody level or a > 1 μ g/mL rise in level compared with pre-immunization levels. Pre-immunization levels are those obtained immediately prior to receipt of 23-PPV.) Post-immunization levels will be measured 4 and 8 weeks after 23-PPV administration for Groups A1, A2, and B.
 - The proportion of patients in Groups A (A1 and A2) and B with a positive response against at least 2 out of 23 pneumococcal antibody serotypes measured 4 weeks after administration of 23-PPV vaccine.
 - The proportion of patients in Groups A (A1 and A2) and B with positive responses against at least 50% of the serotypes (≥ 12 of 23) measured 4 weeks after administration of 23-PPV vaccine.
 - Mean levels of anti-pneumococcal serotype-specific antibody in patients in Groups A (A1 and A2) and B measured immediately prior to and 4 and 8 weeks (which is 4 weeks after Group A1 patients received the 13-PCV booster) after administration of 23-PPV vaccine.
- KLH response:
 - Mean levels of anti-KLH antibody (IgG and IgM) in patients in Groups A (A1 and A2) and B measured immediately prior to the first administration of KLH and 4 weeks after the last administration of KLH.
 - Mean levels of anti KLH antibodies (IgG and IgM) in patients in Groups A (A1 and A2) and B measured over time at 4, 8, and 12 weeks after first KLH administration.

- Strain-specific influenza vaccine response in Groups A2 and B:

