6.4 IMMUNOLOGY ENDPOINTS

6.4.1 Analysis of Immunology Endpoints

Primary Endpoint

The proportion of patients with positive responses to TT vaccine measured 8 weeks after administration of the TT vaccine for Group A and Group B will be assessed.

For patients with pre-immunization tetanus antibody titers <0.1 IU/mL, a positive response to the booster immunization is defined as an antibody titer ≥ 0.2 IU/mL measured 8 weeks after the immunization. For patients with pre-immunization tetanus antibody titers ≥ 0.1 IU/mL, positive response to the booster immunization is defined as a 4-fold increase in antibody titer measured 8 weeks after the immunization. Pre-vaccination levels are those obtained immediately prior to receipt of a vaccine.

Secondary Endpoints

All secondary endpoints are as defined in Section 3.4.2. Descriptive statistical analyses will be used to compare the proportion of patients with responses in the assessments and groups as specified in that section. The mean level of antibody parameters will be presented using geometric means.

Exploratory analyses will be performed to assess the possible relationship among measurements, and clinical response and will be specified in the statistical analysis plan.

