5/Statistical Analysis Plan BN29739

Clinical Study Report: ocrelizumab - F. Hoffmann-La Roche Ltd
Protocol BN29739 Report Number 1079337

1. **BACKGROUND**

This Phase IIIb, multicenter, randomized, open-label study is designed to evaluate immune response to vaccines in patients with relapsing forms of multiple sclerosis (MS) after administration of a dose of ocrelizumab.

The clinical cutoff date (CCOD) will be the earliest date on which all randomized patients will have completed the Week 24 visit for Group A, completed the Week 12 visit for Group B, or prematurely discontinued during the Immunization Study Period (ISP) if they have discontinued before the Week 24 visit for Group A or before the Week 12 visit for Group B.

The scope of this statistical analysis plan includes the following:

- The primary analysis of immunology and safety endpoints evaluated in the ISP
- Analysis of all data available at the CCOD from the following periods:
 - The Optional Ocrelizumab Extension (OOE) after completing the ISP
 - The Safety Follow-Up (SFU) Period after the ISP for patients who did not enter the OOE
 - The SFU Period after completing the OOE

2. **STUDY DESIGN**

This Phase IIIb, multicenter, randomized, open-label study is designed to evaluate immune response to vaccines after administration of a dose of ocrelizumab.

The study consists of the following periods: Screening, an ISP, an OOE, SFU, and a Continued B-cell Monitoring Period.

Following screening, approximately 100 adult patients will be randomized into Groups A and B (2:1 active:control) to compare responses to immunization. Patients in Group B are to receive immunization with tetanus toxoid (TT)-containing adsorbed vaccine, 23-valent pneumococcal polysaccharide vaccine (23-PPV), influenza vaccine, and repeated administration with keyhole limpet hemocyanin (KLH). Group B patients will not receive ocrelizumab, but will remain treatment-naïve or continue with interferon beta (IFN- β) treatment until optional ocrelizumab treatment at the end of the ISP.

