2.1 PROTOCOL SYNOPSIS

The Protocol Synopsis is in [Appendix 1](#). Please note that, in the event that the version of the protocol synopsis in [Appendix 1](#) differs from the version in the current protocol, then the version in the current protocol takes precedence over the version included in this Statistical Analysis Plan (SAP). [Appendix 1](#) will only be updated in the event that the protocol synopsis amended in the future and includes changes that impact this SAP.

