2.2.2 Secondary Outcome Measures

The secondary outcome measures are as follows:

- TT response

The proportion of patients in Groups A (A1 and A2 combined) and B with a positive response (IgG) to TT vaccine measured 4 weeks after booster TT vaccine administration (defined fully in Section [4.4.2.1](#))

Mean levels of anti-tetanus antibody in patients in Groups A (A1 and A2 combined) and B measured immediately prior to and 4 weeks after a booster TT vaccine

- 23-valent pneumococcal polysaccharide vaccine (23-PPV) response and 13-PCV booster response:

The proportion of patients in Groups A1, A2, A (A1 and A2 combined), and B with positive responses against an individual anti-pneumococcal antibody serotype measured 4 weeks after the 23-PPV (23 serotypes) (defined fully in Section [4.4.2.2](#))

The proportion of patients in Groups A1, A2, A (A1 and A2 combined), and B with a positive response against at least 2 out of the 23 serotypes measured 4 weeks after and 8 weeks after administration of the 23-PPV vaccine (defined fully in Section [4.4.2.2](#))

The proportion of patients in Groups A1, A2, A (A1 and A2 combined), and B with positive responses against at least 50% of the serotypes (≥ 12 of 23) measured 4 weeks after administration of the 23-PPV vaccine (defined fully in Section [4.4.2.2](#))

The proportion of patients in Groups A1, A2, A (A1 and A2 combined), and B with positive responses against each of the 23 serotypes measured 8 weeks after patients received the 23-PPV vaccine (which is 4 weeks after Group A1 received the booster 13-PCV) (defined fully in Section [4.4.2.2](#))

Mean levels of anti-pneumococcal antibody (23 serotypes) in patients in Groups A1, A2, A (A1 and A2 combined), and B measured immediately prior to, 4 weeks after and 8 weeks after patients received the 23-PPV (this is 4 weeks after Group A1 received the 13-PCV immunization)

- KLH

Mean levels of anti-KLH antibody (IgG) in patients in Groups A (A1 and A2 combined) and B measured immediately prior to the first administration of KLH and 4 weeks after the last administration of KLH

Mean levels of anti-KLH antibodies (IgG and IgM) in Groups A (A1 and A2 combined) over time at 4, 8, and 12 weeks after first KLH immunization

- Influenza vaccine response:

Proportion of patients in Groups A2 and B who achieve seroprotection defined as specific hemagglutination inhibition (HI) titers >40 at 4 weeks post-immunization

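### The SAP plans one 4-week tetanus proportion where the protocol lists two, without saying so, and plans no geometric mean or confidence interval for the influenza GMT ratio

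*SAP*

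**What the plan says.** **Tetanus at 4 weeks.** Protocol 3.4.2, repeated in the current synopsis, gives two separate items for Groups A and B:

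- the proportion "with a positive response (IgG) to TT vaccine measured 4 weeks after TT vaccine administration";
- the proportion "with a 2-fold increase in tetanus antibody titers, or with tetanus antibody titers" of 0.2 IU/mL or more. The fold rule applies to pre-titres of 0.1 IU/mL or more, and the absolute rule to pre-titres below 0.1.

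Protocol 6.4.1 keeps the full list: "All secondary endpoints are as defined in Section 3.4.2". The protocol defines a tetanus positive response only for the 8-week primary endpoint. For pre-titres of 0.1 IU/mL or more, "positive response to the booster immunization is defined as a 4-fold increase in antibody titers compared with pre-vaccination levels measured 8 weeks after immunization" (Protocol 3.4.1).

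SAP 2.2.2 lists a single 4-week proportion, of patients "with a positive response (IgG) to TT vaccine measured 4 weeks after booster TT vaccine administration". SAP 4.4.2.1 introduces its rule with "Positive response is defined as follows (this differs from the definition of response used for the 8-week assessment above" and then sets a 2-fold rise for pre-titres of 0.1 IU/mL or more, and 0.2 IU/mL or more for lower pre-titres.

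**Influenza GMT ratio.** Protocol 3.4.2 and SAP 2.2.2 both name a strain-specific post:pre GMT ratio. For this ratio SAP 4.4.2.4 specifies mean, median, SD, minimum and maximum. The GMTs in the paragraph just before it receive the SAP 4.4.1 set: geometric means with 95% CIs computed on the log scale and back-transformed, with LLQ/2 imputed at or below the LLQ. Protocol 6.4.1 asks for geometric means when mean antibody levels are presented.

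**The concern.** The first part is a mismatch between documents. Two listed proportions have become one, with no sentence that records the decision. The surviving label, positive response, then means 2-fold at 4 weeks and 4-fold at 8 weeks. Anyone reading the two tables without the SAP's explanatory note could take a change of definition for a change in response. If the protocol meant 4-fold for its first item, that proportion is not planned anywhere in the SAP.

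The second part is a mismatch between a quantity and its summary. A GMT ratio is geometric. The mean and SD of individual post:pre ratios describe something else, which is pulled upwards by the largest fold-rises. The interval a reader would want for the named quantity is not in the plan.

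**Working it through.** The plan gives no figure to reproduce on either point and no SD for any titre. The comparison of texts carries the finding; the arithmetic only shows scale, and every SD below is an assumption.

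**(a) Texts side by side**

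- Protocol 3.4.2, item 1: 4 weeks, positive response, no fold stated.
- Protocol 3.4.2, item 2: 4 weeks, 2-fold, or 0.2 IU/mL or more.
- Protocol 3.4.1: 8 weeks, positive response, 4-fold, or 0.2 IU/mL or more.
- SAP 4.4.2.1: 4 weeks, positive response, 2-fold, or 0.2 IU/mL or more.

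If item 1 meant 2-fold, it would duplicate item 2. The only other fold rule that the protocol attaches to this label is 4-fold. That is an inference, not a stated definition.

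**(a) Scale**

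Take patients with pre-titre of 0.1 IU/mL or more; the rules do not differ below that. Let ln(fold-rise) be normal with SD s. If the 4-fold rate is r, the 2-fold rate is Φ(Φ⁻¹(r) + ln 2 / s). The only planning rate in the documents is 70% (Protocol 6.1, for 8 weeks and the whole group), borrowed here for this stratum. With Φ⁻¹(0.70) = 0.524 and ln 2 = 0.693:

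- s = 0.8: Φ(0.524 + 0.866) = 91.8%, gap 21.8 points
- s = 1.0: Φ(0.524 + 0.693) = 88.8%, gap 18.8 points
- s = 1.5: Φ(0.524 + 0.462) = 83.8%, gap 13.8 points

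With titres unchanged between 4 and 8 weeks, the labelled rate in this stratum would fall by these amounts because of the rule alone. The A minus B difference shows no fixed direction of change. At s = 1.0:

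- A 70%, B 70% under 4-fold: 0 points; under 2-fold also 0
- A 50%, B 70%: −20 points; under 2-fold 75.6 − 88.8 = −13.2
- A 30%, B 50%: −20 points; under 2-fold 56.7 − 75.6 = −18.9
- A 20%, B 40%: −20 points; under 2-fold 44.1 − 67.0 = −22.9

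**(b) Scale**

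For a log-normal ratio, arithmetic mean / geometric mean = exp(s²/2). For n = 33 (the approximate size of Group A2 in Protocol 3.1), the 95% CI of a geometric ratio G is G × exp(±1.96 s/√33). For an illustrative G = 4:

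- s = 0.5: factor 1.13; arithmetic mean 4.53; geometric CI upper limit 4.74
- s = 1.0: factor 1.65; arithmetic mean 6.59; geometric CI 2.84 to 5.63
- s = 1.5: factor 3.08; arithmetic mean 12.32; geometric CI 2.40 to 6.67

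The arithmetic mean passes the upper limit when s²/2 > 1.96 s/√33, that is, when s > 3.92/√33 = 0.68.

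**(b) What the planned output yields**

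Post GMT divided by pre GMT, using the all-nonmissing version with LLQ/2, equals the geometric mean ratio if the same patients contribute to both. The version restricted to values above the LLQ need not use the same patients before and after. The interval needs Var(ln post) + Var(ln pre) − 2 Cov(ln post, ln pre). Separate CIs before and after carry the two variances but not the covariance, so the paired CI cannot be recovered.

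**The case against.** **The SAP is open about its rule.** This stands. SAP 4.4.2.1 says that the 4-week rule differs from the 8-week rule and writes both out. A reader might infer that the SAP conceals a change of definition; it does not. What it leaves unsaid is that two protocol items became one. Where it departs from the protocol on a laboratory listing, SAP 4.6.4.1 says so.

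**Nothing may have been dropped.** A reader might infer that a defined 4-fold endpoint was removed. The protocol ties 4-fold only to 8 weeks, and item 2 could be read as supplying the rule for item 1. That reading makes the two items redundant, so it is less natural, but it is possible. The loss of a 4-fold proportion is therefore conditional on the other reading.

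**The documents may be of different versions.** This is likely. The SAP says: "The study consists of the following periods: Screening, an ISP, an OOE, SFU, and a Continued B-cell Monitoring Period", and the current protocol has removed that monitoring period. Whether the earlier protocol listed both items cannot be checked. The precedence clause in SAP 2.1 does not settle it. It says of the synopsis that, where the two differ, "then the version in the current protocol takes precedence over the version included in this Statistical Analysis Plan (SAP", and it does not extend to the SAP's own analysis sections. The current synopsis lists both items in any case.

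**The GMT ratio is already available.** In part, yes. A reader might infer that it cannot be obtained at all. SAP 4.4.1 puts pre-vaccination geometric means in the same table as the later ones, and the analysis uses completers of the Immunization Study Period, so largely the same patients should contribute. The SAP's list is also worded as what the statistics will include, not as a closed list. The paired CI remains missing; no protocol text demands one.

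**The distortion depends on the chosen SD.** Correct. A reader might infer that the arithmetic mean always falls outside the geometric CI; at SD(ln) 0.5 it does not.

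**Conclusion.** Both parts hold as minor points on secondary, descriptive endpoints. SAP 4.4 plans no hypothesis tests, and the 8-week primary endpoint is defined alike in both documents.

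(a) The firm finding is that the SAP merges two protocol items under one label without declaring it. That this leaves a 4-week 4-fold proportion unplanned rests on the 4-fold reading of the first item. The 14 to 22 point gap rests on a log-normal fold-rise, SD(ln) of 0.8 to 1.5 and a borrowed 70% rate, and applies only to pre-titres of 0.1 IU/mL or more. A reader might infer that the 2-fold rule systematically flatters ocrelizumab. The documents do not support that: the illustrated group difference shrinks, stays the same or grows, depending on the rates.

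(b) The firm finding is the missing paired 95% CI, together with listed statistics that do not themselves give the quantity named. The factor of 1.13 to 3.08 rests on assumed SD(ln) of 0.5 to 1.5.

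**What to change.** (a) In SAP 2.2.2 and 4.4.2.1, name the 4-week tetanus proportions by fold, as SAP 4.4.2.4 already does for influenza. Report both the 2-fold and the 4-fold proportion, each with 0.2 IU/mL or more as the rule for pre-titres below 0.1, and each with the A minus B difference and 95% CI. At the least, state that only the 2-fold rule is used at 4 weeks and that the two items of Protocol 3.4.2 were merged.

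(b) In SAP 4.4.2.4, analyse log(post/pre) per strain and group, with LLQ/2 for values at or below the LLQ as in SAP 4.4.1. Back-transform to a geometric mean ratio with 95% CI, and keep the median.

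The cost is some SAP wording and two small tables from titres already collected; declaring the merger alone needs only wording. Protocol 1.1.4 and 5.1.1.6 already report results from the Immunization Study Period, so any added table should be marked post hoc.
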